More recently, we evaluated the relationship between high b-value diffusion MRI and perfusion MRI (Wahl DR, IJROBP 2016). Of 35 patients with newly diagnosed GBM, the abnormality identified by high b-value diffusion MRI (TV_{HCV}) and that identified by perfusion MRI (TV_{CBV}) defined spatially distinct regions of tumor with mean overlap of only 21%, with 40% of each of these volumes falling outside of the standard gadoliniumenhanced tumor region. On univariate analysis, increasing TV_{HCV} and TV_{CBV} were associated with inferior progression-free survival, while TV_{HCV} was the most important imaging-defined variable associated with inferior progression-free survival on multivariate analysis. On evaluation of patterns of failure, areas of progressive GBM generally coincided with the HCV, CBV or volume of overlap between the two, with the highest positive predictive value (77%) for the percentage of a given volume of interest coinciding with the area of contrast-enhancing progression being the overlap between TV_{HCV} and TV_{CBV} (unpublished data, Figure). Thus, spatially distinct subvolumes of GBM were identified using a combination of advanced imaging technologies that each contained prognostic information, and potentially represent varying biologic phenotypes with distinct genetic alterations that could be use to guide therapy.

[figure not shown]

Figure. MR imaging of pretreatment volumes of interest and correlation to patterns of failure. Prior to radiation (left), underwent conventional T1-post gadolinium contrast imaging to define the volume of abnormal enhancement (Gd). They also underwent high b-value diffusion imaging to determine the hypercellular volume (HCV) and T1-weighted dynamic contrast enhanced perfusion images to define the cerebral blood volume (CBV). Following treatment (right), a multidisciplinary team defined the pattern of failure volume (POFV) where the GBM recurred. Images were co-registered and volumes overlaid to assess overlap.

Summary

Conventional MR imaging is inadequate in defining the extent of tumor growth and highrisk tumor regions that are likely to recur. Advanced imaging techniques such as MET PET and high b-value DW-MRI and perfusion MRI capture tumor extent and identify regions at increased risk for recurrence, and may provide complementary information about the tumor that can be used to direct therapy.

Early imaging changes: Predicting response to therapy

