6.0 RADIATION THERAPY

6.1 Radiation Dose and Fractionation

Radiation therapy will be delivered once daily for a total of 30 fractions, five days per week. If treatment is interrupted due to a non dose-limiting adverse event or any reason other than toxicity, including holidays, weather, transportation, or treatment machine problems, the duration of treatment will be extended accordingly. An initial treatment plan will be designed to simultaneously deliver differing doses per fraction to 2 PTV volumes: 60 Gy to the conventional MRI volume (PTV_Low), which is the volume and dose used in standard practice. An additional simultaneous boost will be delivered to the combination of high b-value diffusion and perfusion abnormality alone (PTV_High, the area assumed to be at highest risk of tumor recurrence).

Patients with a negative postoperative high b-value DW-MRI and perfusion MRI following complete resection will be treated to the post-operative resection cavity and conventional T1 MRI contrast-enhancing region to a total dose of 60 Gy, as per standard of care, and will remain on study to be analyzed with the entire study cohort. A negative high b-value DW-MRI or perfusion MRI will be defined as a combined high b-value DW-MRI and perfusion target volume of 1 cc or less. Radiation dose will be prescribed to ensure that at least 95% of the PTV (D_{95%}) should be covered by 100% of the prescription dose.

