6.3 Treatment Planning and Localization Requirements

Immobilization / Simulation: A treatment planning CT and/or MRI will be obtained with the patient in the same position and immobilization device as for treatment. All patients will be positioned and immobilized with individualized thermoplastic masks to ensure precise localization methods.

Treatment Planning: All patients will undergo MR-guided treatment planning with a high b-value diffusion MRI-defined boost volume. GTV definition, CTV definition, and PTV margin are as described above. CTV and relevant normal tissues will be outlined on planning scan slices. The PTV margins will ensure adequate dose coverage by correcting for variability in treatment set-up and registration variability. Intensity modulated radiotherapy (IMRT) or rapid arc plans will be used to achieve the highest prescription dose to the target, while minimizing dose to the normal brain and other critical structures. The tumor and critical organ constraints are described in further detail below.

Target Volume Coverage: PTV_Low will be treated with a prescription dose of 60 Gy in 2 Gy fractions over 30 fractions, with a minimum dose of 95% of the prescription dose. Additionally, the volume of PTV_Low receiving a dose > 105% of the boost PTV prescription dose will be minimized based on achieving the PTV Low dose prescription requirements.

PTV_High will be treated with a prescription dose of 75 Gy in 2.5 Gy fractions over 30 fractions. Minimum dose to PTV_High will be 95% of the prescription dose, and maximum dose should be no more than 105% of the prescribed dose (no plan that includes any dose greater than 110% will be accepted.)

Organs at Risk: The following critical normal tissues including the brain, brain stem, optic nerves, optic chiasm, and external surface will be outlined on the appropriate MRI/CT scans. Any compromises to the target because of physician decision to spare visual pathway or brainstem will be well-documented.

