11.5 Secondary objective: To assess the ability of post-treatment advanced MRI to distinguish true progression from pseudoprogression

Patients will undergo follow-up advanced MRI (including high b-value MRI) within 1-4 months after completion of chemoradiation. Pseudoprogression is the appearance of progression later determined to be treatment effect, rather than actual progression, and typically occurs within the first 3 months after chemoradiation. True progression status at 12 months will be centrally reviewed by a team of neuro-oncologists, neurosurgeons, neuro-radiologists and radiation oncologists. This gold standard assessment at 12

months will identify patients as 'progressors' or 'non-progressors'. There are several ways to analyze this data. In the first, we will simply assess to what extent the advanced MRI imaging metrics obtained shortly after treatment (1-4 months) can predict the true progression status at 12 months. Because there is little uncertainty surrounding patients who have not progressed at 12 months, the second analysis will only involve apparent 'progressors' at 12 months. The outcome will still be the true (or at least gold standard) assessment of progression status at 12 months and the predictors will again be advanced MRI metrics obtained shortly after treatment. This analysis will directly assess the extent to which the advanced MRI imaging can distinguish 'true' from 'pseudo' progressors. Standard ROC type metrics will be reported, including AUC, sensitivity, specificity as well as negative and positive predictive value for defined thresholds. The key metric from the high b-value MRI and perfusion is the quantity of 'abnormal volume'. Although multiple thresholds will be studied we will consider less than 1 cc abnormal volume on 3 month follow-up high b-value MRI and perfusion to be indicative of pseudoprogression whereas >1 cc abnormal volume will be considered indicative of true progression. While of great clinical interest, the proposed study is not powered to provide definitive answers to these questions and these analyses will be hypothesis generating.

11.6 Secondary objective: To provide descriptive data regarding neuro-cognitive function, health-related quality of life and symptoms related to radiation dose received.

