Patients will complete neurologic exam, mini mental status exam and EORTC global QOL questionnaire and specific brain module and MDASI-BT before, during and after treatment. The results will be summarized descriptively over time as well as by radiation dose. The relation between these outcomes and survival will be assessed by using QOL numbers as (possibly time dependent) predictors in a Cox regression model. Every effort will be made to avoid missing data. Missing data will be carefully considered as to whether it is missing at random or not. Mixed models with subject level random effects can provide valid estimation and inference under certain patterns of informative missingness and will be utilized where warranted. We will also perform simple checks whether for example subjects with decreased QOL are more likely to drop out. For example, we will compare observed QOL at time t amongst patients who did or did not drop out (i.e. decline to provide QOL data) by time t+1.

11.7 Interim analysis:

Due to a possible increased incidence of grade 3 or higher CNS toxicity (possibly, probably, or definitely related to treatment), we will analyze the data 6 months after the 20th patient completes radiation. At this point approximately 29 patients, out of the planned total of 40 patients eligible for radiation boost, will have been enrolled on the trial. It is possible that 6 patients will experience toxicity prior to this time point, in which case, the trial would be halted as soon as the 6th patient experiences toxicity. If the number of patients, out of the first 20, with toxicity (as defined above) is 6 or greater, the trial will be stopped due to possible safety concerns. The operating characteristics of this stopping rule are given in Table 1 below. When the true toxicity rate is 10%, just

1% of trials will stop early. On the other hand, if the probability of toxicity is 40%, 87% of trials will stop early. We note here that we do not expect to see excessive toxicity in this study because the volume of brain treated with the experimental (boost) dose of radiation will be limited to 1/3 the volume of brain, shown to be safe based on our prior dose-escalation study based on standard MRI alone.³⁰

Table 1. The proportion of trials stopping

True P(tox)	10%	20%	30%	40%
Proportion of	1%	20%	58%	87%
Trials				
Stopping				
Early				

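### Section 11.6 summarizes quality of life, symptoms and cognition by radiation dose, but residual imaging volume decides who is boosted and how large the boost is, so a dose pattern could not be separated from tumor burden

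*Combined protocol and SAP*

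**What the plan says.** **The analysis.** Section 11.6 states its aim as "To provide descriptive data regarding neuro-cognitive function, health-related quality of life and symptoms related to radiation dose received". Its plan for these data is: "The results will be summarized descriptively over time as well as by radiation dose". It does not define dose (prescribed, boost-volume or brain dose). It names no adjustment or stratification by residual tumor volume, extent of resection or baseline score. It does name mixed models with subject-level random effects, in the context of missing data.

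**How dose is set.** Section 6.1 says that patients with negative diffusion and perfusion imaging after complete resection "will be treated to the post-operative resection cavity and conventional T1 MRI contrast-enhancing region to a total dose of 60 Gy". It defines negative as a "combined high b-value DW-MRI and perfusion target volume of 1 cc or less". These patients "will remain on study to be analyzed with the entire study cohort". For the rest, 6.3 says: "PTV_High will be treated with a prescription dose of 75 Gy in 2.5 Gy fractions over 30 fractions". The sample-size text in 11.1 uses the same 1 cc cut to define who is eligible for the boost.

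**How the boost volume is set.** Under 6.2, PTV_High is the diffusion/perfusion abnormality with a margin of 0.3 to 0.6 cm, or as appropriate.

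**What the protocol says about that volume.** The Introduction reports, from 35 earlier patients, that larger diffusion and perfusion volumes "were associated with inferior progression-free survival".

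**The concern.** A summary by dose is useful only if patients at different doses are otherwise similar, or if the differences are taken into account. Here the imaging finding that measures residual disease also decides whether a patient is boosted and how much tissue receives the boost. A patient with more residual tumor gets more high-dose volume by design, and may have worse function because of the tumor.

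Section 11.3 meets a similar problem when it compares recurrence between subvolumes. It names volume and dose as potential confounders and proposes weighting by volume and stratifying on dose. Section 11.6 has no counterpart.

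At stake is how the functional results are read. The Introduction stresses keeping toxicity no worse than with standard therapy, and the trial is meant to inform whether a randomized trial should follow. A table of cognition or symptoms by dose will tend to be read as evidence on what the boost does to function, and as planned it could not serve as that.

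**Working it through.** The plan gives no figure on this point. The check traces how dose arises under three readings of dose and then sizes the problem with stated assumptions.

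**1. Prescribed dose**

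Inputs: 60 Gy only at 1 cc or less after complete resection (6.1); 75 Gy for every boosted patient (6.3); boost eligibility above 1 cc (11.1).

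There are two planned levels, and they do not overlap in residual volume. Among the 40 boosted patients (80 with the second center) the prescription does not vary, so all the contrast comes from the 60 Gy-only group. The documents do not give that group's size. If its share of all patients is s and k are boosted, its size is k × s/(1−s). With s assumed between 5% and 20%:
- k = 40: 40 × 0.05/0.95 = 2.1, up to 40 × 0.20/0.80 = 10.
- k = 80: 4.2 up to 20.

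Now suppose dose has no effect and the score depends only on log residual volume, with correlation ρ (assumed; the documents give none). For a normal log volume cut at quantile s, the expected 75-minus-60 Gy difference in SD units is −ρ × φ(z_s)/[s(1−s)]. At s = 10% this is −ρ × 0.1755/0.09 = −1.95ρ. Simulation with 400,000 draws agrees to within 0.01:

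| ρ | s = 5% | s = 10% | s = 20% |
|---|---|---|---|
| 0.1 | −0.21 | −0.20 | −0.18 |
| 0.2 | −0.44 | −0.39 | −0.34 |
| 0.3 | −0.65 | −0.58 | −0.53 |
| 0.5 | −1.09 | −0.97 | −0.87 |

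The contrast would also be noisy. Its standard error is about √(1/n60 + 1/40): √(1/10 + 1/40) = 0.35 SD with 10 unboosted patients, and √(1/2 + 1/40) = 0.72 SD with 2.

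**2. Boost volume**

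For a spherical target of volume V, r = (3V/4π)^(1/3) and PTV_High = (4/3)π(r + m)³, with m = 0.3 or 0.6 cm (6.2).

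| V (cc) | PTV_High, m = 0.3 | PTV_High, m = 0.6 | Shell outside the abnormality |
|---|---|---|---|
| 2 | 5.3 | 11.0 | 3.3 to 9.0 |
| 10 | 18.4 | 30.4 | 8.4 to 20.4 |
| 40 | 59.5 | 84.4 | 19.5 to 44.4 |

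In an assumed population (V log-normal, median 10 cc, log SD 0.8, V above 1 cc; margin uniform from 0.3 to 0.6 cm), log V and log PTV_High correlate 0.968.

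**3. Brain dose**

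Some brain dose does not come from residual tumor. GTV_Low includes the surgical cavity, and CTV_Low and PTV_Low add 1.7 and 0.3 cm (6.2). Targets may be compromised to spare the visual pathway or brainstem (6.3). Using 60 × PTV_Low + 15 × PTV_High as a rough integral dose, with PTV_Low grown by 2.0 cm from residual plus an independent cavity (log-normal, median 25 cc, log SD 0.6, assumed), its log correlates 0.542 with log V.

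**4. What adjustment would cost in precision**

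Adjusting for a covariate with correlation c multiplies the standard error of the dose slope by about 1/√(1−c²), apart from any residual variance the covariate explains.
- Boost volume: 1/√(1 − 0.968²) = 1/√0.063 ≈ 4.0.
- Brain dose: 1/√(1 − 0.542²) = 1/√0.706 ≈ 1.19.

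Under these assumptions adjustment is feasible for a brain-dose measure and close to useless for boost volume.

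**The case against.** The strongest reply is that 11.6 is descriptive. Objective 2.2.5 does not mention dose at all, no test or decision rule depends on these summaries, and no causal claim is made. Baseline scores are collected (4.3, 4.7) and results are shown over time, so change from baseline will be visible. This stands as a limit on the importance of the point. It does not remove it, because 11.6 itself ties the outcomes to dose received and gives the reader no warning.

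A second reply is that dose received more naturally means dose to brain, as in the group's earlier white-matter work described in the Introduction, and brain dose is not simply tumor volume. This also stands in part. The margin alone can reverse the order: the shell around a 2 cc residual at 0.6 cm (9.0 cc) exceeds that around 10 cc at 0.3 cm (8.4 cc). Confounding of brain dose is therefore partial, which is why an adjusted analysis is possible.

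A reader might go further and infer that any dose pattern would really be a tumor-burden pattern, or that worse scores at 75 Gy are bound to appear. The documents support neither. Failure to separate two causes does not show which one is at work, and both may contribute. The prognostic finding quoted concerns progression-free survival; the protocol reports no relation between residual volume and quality of life, symptoms or cognition. Nor are 60 Gy-only patients strictly free of abnormality, since up to 1 cc is allowed.

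Finally, the mixed models in 11.6 are named for missing data, not for dose effects. That is true. Adding two covariates that are already collected extends their use without requiring a new kind of analysis.

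**Conclusion.** The point holds as a limit on interpretation. As planned, a relation between dose and function in 11.6 could not be separated from tumor burden. The confounding is complete for prescribed dose, nearly complete for boost volume (log correlation about 0.97) and partial for brain dose (about 0.54). The first follows directly from 6.1, 6.3 and the boost-eligibility cut in 11.1. The two correlations depend on assumed distributions of residual volume, margin and cavity, and on spherical targets.

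With no true dose effect, the apparent deficit at 75 Gy would be about 0.2 SD if residual volume correlated 0.1 with the score, and 0.53 to 0.65 SD if it correlated 0.3. These sizes are illustrations. They rest on an assumed correlation and an assumed 60 Gy-only share of 5% to 20%, and the small unboosted group would make any observed difference very uncertain.

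The analysis is secondary and descriptive. The primary 12-month survival test is not affected.

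**What to change.** Amend 11.6 as follows.

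- **Dose measure.** Among boosted patients, relate scores to one prespecified brain-dose measure from the existing treatment plans, for example mean dose to brain outside PTV_High. Brain is already outlined under 6.3.
- **Model.** Use the mixed model already named, with baseline score and baseline combined diffusion/perfusion volume as covariates. Both are available from the pretreatment assessments and target definition. Show the unadjusted descriptive summary beside it.
- **60 Gy-only patients.** Present them as a separate group, and state that their contrast with boosted patients is not a dose comparison.
- **Label.** Call the adjusted dose estimate exploratory.

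The cost is a change of wording and an export of dose data already held in the plans. Treatment, assessments and sample size are unchanged. The downside is precision: brain dose and residual volume are correlated, so with about 40 boosted patients, and fewer at later visits, the adjusted estimate will be imprecise. Adjustment also removes only the burden that baseline imaging volume and baseline score capture.

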2.1 Primary Objective

To estimate 12-month overall survival (OS) of GBM patients treated with high-dose RT based on high b-value DW-MRI and perfusion MRI planning, with concurrent temozolomide, in relation to historical controls

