11.0 STATISTICAL CONSIDERATIONS

This is a study of concurrent temozolomide and high dose radiation using biologic based target volume definition in patients with newly diagnosed glioblastoma (GBM).

The overall goal of this study is to determine if the treatment regimen described in this protocol is sufficiently promising to advance to a definitive randomized trial. Treatment for patients treated under this protocol will differ from standard care in the following ways:

- 1) High b-value diffusion-weighted and perfusion MRI will be used in target volume definition
- 2) The radiation dose to the boost volume will be 75 Gy based on earlier data demonstrating the safety and potential efficacy of this approach.
- **11.1** Primary objective: To improve overall survival at 12 months compared with published historical controls.

The final test addressing this aim will occur when the last enrolled patient completes 12 months of follow-up. If patients drop out or are lost to follow-up prior to 12 months, we will utilize the Kaplan-Meier approach to estimate OS at 12 months. Otherwise we will use the simple binomial proportion of patients who are alive within 12 months of treatment. We will test the null hypothesis that the true 12 months OS is equal to 0.65, based on recently reported survival rates from RTOG 0525 and RTOG 0825. The alternative hypothesis will be that 12 months OS is greater than 0.65. The test will be one-sided at an alpha=0.10 level. We will additionally use the Kaplan-Meier approach to estimated OS over time for all patients and according to MGMT and IDH1 status.

For example, MGMT status is an established prognostic factor in this setting with hazard ratios of approximately 2 for an endpoint of overall survival. On average we would expect a similar proportion of methylated patients in this trial as was observed for RTOG 0525 and RTOG 0825 (30%). However, with a sample size of 40, it is possible that the proportion of methylated patients will differ from 30% by a non-negligible amount. To account for this in the statistical analysis, we will weight patients so that the

weighted proportion of methylated patients is equal to 30%. Specifically, if p* denotes the observed proportion of methylated patients in this trial, the new weights will be .3/p* for methylated patients and (1-.3)/(1-p*) for unmethylated patients.

Sample size considerations:

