We anticipate enrolling 40 patients eligible to undergo a boost of radiation (>1 cc combined high b-value DW-MRI and perfusion MRI abnormality) at our institution. A similar protocol will be opened at a second center and treat an additional 40 patients in an identical fashion. This approach was chosen over a single multi-institutional trial protocol for logistical and financial reasons. Nevertheless, we expect to jointly analyze the data from all 80 patients following trial completion. Center will be included as a stratification variable in the analyses. Allowing for 10% of these patients to be non-evaluable for the primary endpoint, 40 (80) enrolled patients will provide greater than 80% power to detect an improvement in 12 month OS from 65% (based on historical controls) to 82% (40 patients) or 78% (80 patients). These results are based on an exact 1-sided test at alpha=0.10. Once completed, this trial will determine if the treatment is sufficiently promising to warrant further investigation in a multi-center, randomized trial.

11.2 Secondary objective: To estimate progression-free survival, patterns of failure and response rates in relation to values from historical control patients.

Progression Free Survival is defined as the time from study enrollment till the first of death from any cause or progression. Kaplan-Meier estimates of PFS will be generated for all patients on this trial and according to MGMT/IDH1 status. Additionally we will compare the observed PFS at 6 months and 1 year to published values from historical control patients.

Patterns of failure and response rates - Failures will be classified as central, in-field, marginal or distant, based on previously published criteria. Our hypothesis is that including high b-value diffusion and perfusion MRI in treatment planning will reduce the proportion of central failures within the high-dose radiation region. We will explore whether this appears to be the case by comparing this proportion to prior dose escalation studies based on conventional MRI planning alone.

Response rates - The proportion of complete, partial and any responders will be calculated along with 95% likelihood ratio confidence intervals using RANO criteria. The proportion of any responders will also be compared to published values from historical controls.

11.3 Secondary objective: Assess the ability of pre-therapy and week 3 MET PET scans and advanced MRI to determine sub-volumes at high risk of recurrence.

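### Section 6.1 analyses unboosted 60 Gy patients with the whole cohort, but the objective and power concern boosted or boost-eligible patients, and neither the 11.1 test nor the 11.7 stopping rule states its set

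*Combined protocol and SAP*

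**What the plan says.** - **Section 6.1** gives unboosted patients (combined volume of 1 cc or less, following complete resection) 60 Gy and states that they "will remain on study to be analyzed with the entire study cohort".
- **Section 2.1** sets the primary objective: "To estimate 12-month overall survival (OS) of GBM patients treated with high-dose RT".
- **Section 11.1, sample size**: "We anticipate enrolling 40 patients eligible to undergo a boost of radiation (>1 cc combined high b-value DW-MRI and perfusion MRI abnormality". Power is quoted for 40 such patients, or 80 with the second centre, after a 10% loss.
- **Section 11.1, test**: if nobody is lost before 12 months, "Otherwise we will use the simple binomial proportion of patients who are alive within 12 months of treatment". No set is named. The null value of 0.65 is "based on recently reported survival rates from RTOG 0525 and RTOG 0825". The MGMT weights use p*, which "denotes the observed proportion of methylated patients in this trial". The text leading to those weights mentions a sample size of 40.
- **Section 11.1, display**: an additional Kaplan-Meier analysis covers "estimated OS over time for all patients and according to MGMT and IDH1 status". No breakdown by boost status is planned.
- **Section 11.7**: "we will analyze the data 6 months after the 20th patient completes radiation", with stopping if 6 or more of the first 20 have grade 3 or higher CNS toxicity possibly, probably or definitely related to treatment. The planned 40 are called boost-eligible there; the 20 are not.
- **Section 1.0 (second Summary) and section 6.3** say that all patients receive the higher dose or boost-volume planning, without the 6.1 exception.

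**The concern.** The survival test supports one go/no-go decision on a randomised trial, and two analysis sets can be defended from the text. If 6.1 is followed, the quoted power does not describe the set tested. If the boost-eligible set is used, 6.1 is not followed. The MGMT weights change with the set as well. Leaving the choice until data are seen makes it possible for the choice to change the result.

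The same gap matters for safety. The interim rule exists because the boost may raise CNS toxicity. Any patients not given the boost who count among the 20 could dilute the rule, and Table 1 would then no longer describe the boost.

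**Working it through.** **Inputs from the plan.** Null 0.65; exact one-sided test at 0.10; alternatives 0.82 (40 enrolled) and 0.78 (80 enrolled); 10% non-evaluable, so 0.9 × 40 = 36 and 0.9 × 80 = 72; stop at 6 or more of 20.

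**Assumed, because the documents give no values.** The number of unboosted patients k, their 12-month survival (65-85%) and their toxicity (0-10%). MGMT weighting, centre stratification and censoring are ignored.

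**1. The plan's own figures.** The cut-off c is the smallest value with P(Bin(n, 0.65) ≥ c) ≤ 0.10.
- n = 36: c = 28, size 7.3%, power at 0.82 is 81.3%.
- n = 72: c = 53, size 7.7%, power at 0.78 is 85.1%.
- P(Bin(20, p) ≥ 6) for p = 10, 20, 30, 40% is 1.1, 19.6, 58.4, 87.4%, which matches Table 1.

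All of these treat every patient as boosted.

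**2. Whole-cohort test.** Add k unboosted patients, recompute c for n + k, and take P(Bin(n, p_boosted) + Bin(k, p_unboosted) ≥ c).

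| Set (unboosted share) | Cut-off | Boosted at 65%, unboosted at 75-85% | Boosted at alternative, unboosted at 65% / 85% |
|---|---|---|---|
| 36 + 2 (5%) | 29/38 | 11-12% | 83% / 87% |
| 36 + 4 (10%) | 31/40 | 8-10% | 75% / 84% |
| 36 + 9 (20%) | 34/45 | 14-21% | 76% / 92% |
| 72 + 4 (5%) | 56/76 | 8-10% | 82% / 87% |
| 72 + 8 (10%) | 58/80 | 13-18% | 85% / 93% |
| 72 + 18 (20%) | 65/90 | 17-29% | 80% / 96% |

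The third column is the chance of declaring the regimen promising when 65% holds for boosted patients and the boost adds nothing. Some row-to-row differences come from the discrete cut-offs: 36 + 2 with unboosted at 65% has more power than 36 boosted alone.

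**3. If 65% instead describes a mixed population.** With unboosted survival at 85%, the null rate in boosted patients is (0.65 × (36 + k) − 0.85k)/36, and power is taken 0.17 above it.
- k = 9: (29.25 − 7.65)/36 = 0.600. Whole-cohort test: size 8.5%, power 76%. Boost-eligible test: 2.0% and 55%.
- k = 4: (26 − 3.4)/36 = 0.628. Whole cohort: 6.3% and 75%. Boost-eligible: 4.2% and 70%.

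**4. Chance that the two sets give different decisions.** Sum the probability over outcomes where the 28/36 rule and the pooled rule disagree, with unboosted survival at 65-85%.
- k = 4: 3-4% with boosted at 65%, 6-10% with boosted at 82%.
- k = 9: 6-14% and 10-13%.

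**5. Stopping rule with u unboosted among the 20.** P(Bin(20 − u, p) + Bin(u, q) ≥ 6), with q = 0 to 0.10.

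| Boosted toxicity | u = 0 (Table 1) | u = 2 | u = 4 |
|---|---|---|---|
| 30% | 58% | 47-51% | 34-42% |
| 40% | 87% | 79-81% | 67-73% |

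**The case against.** Section 6.1 can be read as a prespecified rule: image everyone, boost those with a target, analyse all. The sample-size sentence would then be an accrual target, and the defect would shrink to power not restated for the larger set. That reading is coherent. It still leaves 2.1 and the power statement describing a different set, and the sample size of 40 mentioned in 11.1 points indirectly to the boost-eligible patients. The reference to all patients in 11.1 does not settle it, because it belongs to the additional Kaplan-Meier display and not to the test.

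On 11.7, the natural reading is that the 20 are boosted: the planned 40 are called boost-eligible and the safety argument concerns the boost volume. That stands, so the point there is to make the wording match the intent.

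The statements in 1.0 and 6.3 can be taken as the general case with 6.1 as the specific exception. They are minor.

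A reader might infer that pooling inflates the false-positive rate. The documents do not support that. Section 1.0 links larger imaging volumes to worse progression-free survival in 35 patients, which is only indirect evidence that unboosted patients live longer. Nothing says that the 65% applies to boost-eligible patients; if the control is unselected, the whole-cohort test is not inflated and the boost-eligible test is the conservative one.

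**Conclusion.** The point stands as a conflict between sections, and should be fixed. Confidence is high for the conflict in the text, not for any direction or size of bias. The quoted power and Table 1 are not wrong: they are correct for an all-boosted set. What is missing is a statement that this is the set to be tested and counted.

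For a single centre, the error rate stays near nominal at unboosted shares of 10% or less (8-12%). In the joint analysis, 72 + 8 gives 13-18% if unboosted survival is 75-85% and 65% holds for boosted patients. Larger effects need shares of 20% or more, which no document supports. The stopping-rule dilution (87% to 79-81% or 67-73% at a 40% boosted rate) rests on 2 or 4 of 20 being unboosted with 0-10% toxicity, and arises only if 11.7 is applied literally.

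**What to change.** 1. **Section 11.7.** Define the trigger as the 20th boosted patient and the denominator as the first 20 boosted patients, so that Table 1 applies to the boost. Cost: a slightly later interim look. At an assumed 10% unboosted share, 20/0.9 ≈ 22 treated patients are needed; at 20%, 20/0.8 = 25.
2. **Section 11.1.** Before data are seen, name one analysis set for the 12-month survival test, compute the MGMT weights in that set, and report the other set beside it. State as an assumption which population the 65% describes.
   - If the whole cohort of 6.1 is kept: say that the quoted power applies to boost-eligible patients only, restate it for the whole cohort under an assumed unboosted share, and add the boost-eligible estimate.
   - If the boost-eligible set is chosen: amend 6.1, and note that the test is conservative if the 65% describes a mixed population.
3. **Sections 1.0 and 6.3.** Reconcile the statements about all patients with the exception in 6.1 (minor wording).

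No new data or visits are needed.
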